3.3.4 Removal of subjects from therapy or assessments

3.3.4.1 Removal of individual subjects

An individual patient must be withdrawn from the treatment if:

- The patient withdraws consent, without the need to justify the decision.
- The patient needs any invasive procedure such as cataract surgery, laser photocoagulation or retinal surgery during the study period.
- The patient needs any invasive procedure as cardiac catheterism or stent.
- The patient becomes pregnant during the trial. Patient will be followed up until birth or otherwise termination of the pregnancy.
- The patient needs to take concomitant drugs that interfere with the investigational product(s), in the clinical judgment of the investigator.
- The patient is no longer able to participate for other medical reasons (e.g. surgery, AEs, or other diseases).
- The patient needs to stop all current antipsychotic or concomitant psychotropic medications.
- The patient's disease state dramatically worsens, in clinical judgment of investigator.
- The patient experiences clinically significant loss of visual acuity and/or any ocular symptoms/signs attributable or not to the study medication, by the investigator's judgment (e.g. acute loss of vision ≥ 5 letters, new macular changes such as intra- or sub-retinal fluids or haemorrhage, etc.).
- The patient exhibits suicidality, in the clinical judgment of the investigator or according to criteria below:
 - Any suicidal behavior (i.e. actual attempt, interrupted attempt, aborted attempt, or preparatory acts or behavior)
 - Any suicidal ideation of type 4 or 5 in the C-SSRS (i.e. active suicidal thought(s) with intent but without specific plan, or active suicidal thought(s) with plan and intent).

A patient can be discontinued from treatment after discussion between sponsor and investigator if eligibility criteria are being violated, or if the patient fails to comply with the protocol (e.g. non-attendance at study assessments).

Subjects who discontinue participation after signing the informed consent form but prior to randomization (Visit 2) will be considered screening failures. For screening failure subjects, the demographic, AE, concomitant medication and randomization eCRFs in RDC must be completed. The subjects will be identified as screen failures in the randomization eCRF and no further follow-up is required. SAEs occurring in subjects after having discontinued in the study due to screening failures, and who did not receive any study medication, do not need to be reported, unless the investigator considers the SAE related to the screening procedures.

Subjects who discontinue or withdraw from the study after randomization (Visit 2) will be considered as "early discontinuations" and the reason for premature discontinuation must be recorded in the eCRFs (cf. Section 6.2.3 for early discontinuation procedures). The data will

Boehringer Ingelheim 22 February 2017 BI Trial No.: 1289.27

Doc. No.: c02218444-07 Trial Protocol Revision 3 Page 33 of 101

be included in the trial database and will be reported. Subjects who withdraw or discontinue from the trial after randomization will not be replaced.

3.3.4.2 Discontinuation of the trial by the sponsor

Boehringer Ingelheim reserves the right to discontinue the trial overall or at a particular trial site at any time for the following reasons:

Failure to meet expected enrolment goals overall or at a particular trial site,

Emergence of any efficacy/safety information that could significantly affect continuation of the trial,

Violation of GCP, the approved CTP, or the contract by a trial site or investigator, disturbing the appropriate conduct of the trial.

The investigator / the trial site will be reimbursed for reasonable expenses incurred in case of trial termination (except in case of the third reason).

BI Trial No.: 1289.27

Doc. No.: c02218444-07 Trial Protocol Revision 3 Page 34 of 101

4. TREATMENTS

4.1 TREATMENTS TO BE ADMINISTERED

BI 409306, as a film-coated tablet, will be produced by Boehringer Ingelheim Pharma GmbH & Co. KG. Each film-coated tablet contains 25 mg or 50 mg BI 409306, or matching placebo blistered in 7-count Alu blister strips.

Eligible subjects will be assigned to each treatment group (25 mg or 100 mg) alternatively in the order that they randomized (cf. Section 3.1 and Section 3.3.2).

4.1.1 Identity of BI investigational product and comparator product

The following table summarizes the information about the investigational products as used in this trial:

Table 4.1.1: 1 BI 409306, 25 mg and 50 mg

Substance:	BI 409306
Pharmaceutical form:	Film-coated tablet
Manufacturer:	Boehringer Ingelheim Pharma GmbH & Co. KG
Unit Strength:	25 mg, 50 mg
Daily dose:	25 mg q.d. or 100 mg q.d.
Route of administration:	Per os (oral)
Posology:	Once daily
Duration of use:	14 days

Table 4.1.1: 2 Placebo matching BI 409306, 25 mg and 50 mg

Substance:	BI 409306
Pharmaceutical form:	Film-coated tablet
Manufacturer:	Boehringer Ingelheim Pharma GmbH & Co. KG
Unit Strength:	N/A
Daily dose:	N/A
Route of administration:	Per os (oral)
Posology:	Once daily
Duration of use:	14 days

Doc. No.: c02218444-07 Trial Protocol Revision 3 Page 35 of 101

4.1.2 Method of assigning subjects to treatment groups

Subjects eligible for the trial will be assigned at random in a 1:1 ratio of 25 and 100 mg dose per group at Visit 2 (cf. Section 3.1). Details on randomization are provided in Section 7.5. Assignment to the treatment groups will be determined at the site by having the next lowest sequentially numbered medication kit within each subject population group assigned (AD group, CIAS group, HV/AD low age group, HV/AD high age group, HV/CIAS low age group, HV/CIAS high age group). The assigned medication number will be entered in the eCRF and the corresponding medication kit should be given to the patient/healthy volunteer.

Using this procedure, the Investigator and study staff will be blinded to the assignment to which the patient was randomized. Note that the medication numbers assigned to the patient are different from the patient number.

4.1.3 Selection of doses in the trial

According to the result of previous trials, BI 409306 was well tolerated in young and elderly healthy subjects in single doses of 0.5 to 350 mg and multiple doses up to 100 mg once daily. The doses selected for this trial cover the estimated therapeutic range and include a safety margin (cf. Section 1.2).

4.1.4 Drug assignment and administration of doses for each patient

Patient/healthy volunteer will be assigned study medication and the first dose administered on site at Visit 3, Day 1. Other doses may be administered at home, according to the home visits optional schedule as specified in the Flow Chart. Each patient/healthy volunteer will be administered three tablets, one from each blister dispensed. Table 4.1.4: 1 outlines the treatment and administration of dose for each patient/volunteer.

Treatment Group	Total Drug Administered	Packaging
BI 409306 25 mg	BI 409306 25 mg active	Orange-Label 25 mg Blister
	BI 409306 50 mg matching PBO BI 409306 50 mg matching PBO	Blue-Label 50 mg Blister
BI 409306 100 mg	BI 409306 25 mg matching PBO	Orange-Label 25 mg Blister
	BI 409306 50 mg active BI 409306 50 mg active	Blue-Label 50 mg Blister

The study medication will be administered with about 240 mL of water in the sitting/standing position under supervision of the investigating physician or designee.

Doc. No.: c02218444-07 Trial Protocol Revision 3 Page 36 of 101

Subjects are not allowed to lie down during the 2 hours following drug administration except for medical examination. They are not allowed to sleep. Water is allowed ad libitum except for one hour before and after drug administration. During in-patient, standardized meals will be served at 1, 5 and 10 hours (\pm 1 hour) following drug administration post dose on days 1 and 14. Additionally, snacks will be served at 7 hour and 13 hour (\pm 1 hour) post dose on all days. The time of last meal before drug administration will be recorded on PK blood draw Days 1 and 14.

The actual date and time of administration of the medication at the trial visit will be recorded in the eCRF.

4.1.5 Blinding and procedures for unblinding

4.1.5.1 Blinding

Subjects, investigators and everyone involved in analysing or with an interest in this double blind study will remain blinded with regard to the randomized treatment assignments until after database lock.

The randomization code will be kept secret by Clinical Trial Support up to database lock. They will only release it in accordance with BI standard operating procedures.

The study will only be unblinded after all Adverse Event (AE) related eCRF / electronic data have been entered into the trial data base and after AE related queries have been resolved.

4.1.5.2 Procedures for emergency unblinding

An emergency code break will be available to the investigator / pharmacist / investigational product storage manager. This code break may only be opened in emergency situations when the identity of the trial drug must be known to the investigator in order to provide appropriate medical treatment or if required to assure safety of trial participants. If the code break for a patient is opened, the sponsor must be informed immediately. The reason for opening the code break must be documented on the envelope or appropriate eCRF page along with the date and the initials of the person who broke the code.

4.1.6 Packaging, labelling, and re-supply

Drug supplies will be provided by the Department of Pharmaceutical Development of Boehringer Ingelheim Pharma GmbH & Co. KG, Biberach, Germany. The clinical trial supply consists of patient specific kits with trial identification that hold the trial medication. The blister within the clinical trial supply kits are labelled with:

- Trial number
- Name of product and strengths
- Pharmaceutical dosage form, quantity of dosage units
- Route and mode of administration
- Term "for clinical trial use"
- Sponsor name and address

Proprietary confidential information.

Doc. No.: c02218444-07 Trial Protocol Revision 3 Page 37 of 101

- Storage conditions
- Use by date
- Medication number
- Batch number

Label examples are given in the Investigator Site File (ISF).

All drug supplies will be shipped to sites in the initial shipment with re-supply as needed.

For details of packaging and samples of the label, refer to the ISF.

4.1.7 Storage conditions

Drug supplies will be kept in their original packaging under the labeled storage conditions. The trial medication must be stored securely, e.g. in a locked cupboard or at a pharmacy. It may only be dispensed to trial subjects according to the protocol by authorized personnel as documented in the Trial Staff List in the ISF.

All unused medication must be returned to the sponsor. Receipt, usage and return must be documented on the respective forms. Account must be given for any discrepancies.

4.1.8 Drug accountability

Drug supplies, which will be provided by the sponsor, must be kept in a secure, limited access storage area under the storage conditions defined by the sponsor. A temperature log must be maintained to make certain that the drug supplies are stored at the correct temperature.

The investigator / pharmacist / investigational product storage manager will receive the investigational products delivered by the sponsor when the following requirements are fulfilled:

- approval of the study protocol by the IRB / ethics committee,
- availability of a signed and dated clinical trial contract between the sponsor and the Head of Trial Centre,
- approval/notification of the regulatory authority, e.g. competent authority,
- availability of the curriculum vitae of the principal investigator,
- availability of a signed and dated clinical trial protocol or immediately imminent signing of the clinical trial protocol
- availability of the proof of a medical licence for the principal investigator,
- availability of the FDA Form 1572.

The investigator / pharmacist / investigational product storage manager must maintain records of the product's delivery to the trial site, the inventory at the site, the use by each patient/healthy volunteer, and the return to the sponsor or alternative disposition of unused/expired product(s).

Doc. No.: c02218444-07 Trial Protocol Revision 3 Page 38 of 101

These records will include dates, quantities, batch/serial numbers, expiry ('use by') dates, and the unique code numbers assigned to the investigational product(s) and trial subjects. The investigator / pharmacist / investigational product storage manager will maintain records that document adequately that the subjects were provided the doses specified by the CTP and reconcile all investigational product(s) received from the sponsor. At the time of return to the sponsor, the investigator / pharmacist / investigational product storage manager must verify that all unused or partially used/expired drug supplies have been returned by the clinical trial patient and that no remaining supplies are in the investigator's possession.

4.2 CONCOMITANT THERAPY, RESTRICTIONS, AND RESCUE TREATMENT

4.2.1 Rescue medication, emergency procedures, and additional treatment

There are no special emergency procedures to be followed. No rescue medication, emergency procedure or additional treatment is foreseen for this study.

Throughout the duration of the trial subjects should continue to take their current antipsychotic and concomitant psychotropic medications, the dose of which should remain unchanged unless necessary for the welfare of the patient. These medications will not be provided as part of the clinical trial supplies, unless required by local laws and regulations. Any change in dose of antipsychotic and concomitant psychotropic medications should be recorded in the source documentation and on the appropriate pages of the eCRF.

Any additional treatment that is considered necessary for the patient's/healthy volunteer's welfare may be given at the discretion of the Investigator.

4.2.2 Restrictions

4.2.2.1 Restrictions regarding concomitant treatment

Any medication that may interfere with the action of BI 409306 or whose action may be altered by concomitant administration of BI 409306 during the treatment period and the 14-day follow-up period, in the clinical judgment of the investigator, is not permitted.

Chronic use (\geq 14 days) of topical or systemic corticosteroids is restricted during the study period.

Use of medications that are known to be strong or moderate CYP1A2 inhibitors is not permitted. (For a list of strong and moderate CYP1A2 inhibitors please consult the ISF Section 11 "Safety Information").

No entering or modification of smoking-cessation programs may occur during the conduct of the trial.

Patient will not begin or increase frequency/duration of psychotherapy during the study period, receive electroconvulsive therapy, nor begin any type of non-Western therapies.

For CIAS patients, use of hypnotics and anxiolytics is not prohibited; however, these medications should be administered to patients according the instruction below:

- Long-acting hypnotics and anxiolytics (i.e. Diazepam) are not permitted during the study period.
- Short-acting or intermediate-acting hypnotics and anxiolytics (e.g. lorazepam and zaleplon) are permitted if treated with a stable dose for at least 8 weeks.
- Short-acting hypnotics and anxiolytics are allowed if taken PRN.
- Short-acting or intermediate hypnotics and anxiolytics should not be taken within 8 hours of study procedures.

Also for CIAS patients:

- Use of Clozapine (atypical antipsychotic medication) is not permitted during the study period.
- Anticholinergics are allowed to be used if subjects are on first generation antipsychotics and have been treated at a stable dose for at least 6 months prior to randomisation.
- Antiepileptics and lithium are allowed if initiated at least 6 months prior to randomisation.

For AD patients, intake of the following medications with the mentioned exceptions is prohibited during the entire duration of the trial including follow-up:

- Tricyclic antidepressants, other drugs which are active on the central nervous system (CNS) i.e. psychotropics (tricyclic antidepressants and monoamine oxidase inhibitors, mood stabilisers, neuroleptics, atypical antipsychotics, anti-epileptics, benzodiazepines, other hypnotics or sedatives (including sedative antihistamines), muscle relaxants, or central analgesics, e.g., opioids.
 - Note: Zolpidem (10 mg/day), chloral hydrate (1 g/day), triazolam, quetiapine, temazepam and oxazepam if needed for sleep are allowed as needed. Olanzapine or risperidone are allowed as needed for occasional intake in case of psychotic symptoms.
 - Agents having central dopamine antagonist activity, i.e. reserpine, methyldopa, antiemetic's etc. However, the serotonin and combined serotonin/norepihnephrine Re-Uptake Inhibitors (SSRIs/SNRIs) like fluoxetin, es-citalopram, citalopram, sertalin, venlafaxin, duloxetin are allowed, but paroxetine is excluded. Other antidepressant drugs without anticholinergic effects may be given as needed if the total daily dose was stable 8 weeks prior to randomization and is expected to be maintained for the duration of the trial.
 - Intake of other phospodiesterase inhibitors (for example theophylline, roflumilast, sildenafil, tadalafil, vardenafil, avanafil).

Doc. No.: c02218444-07 Trial Protocol Revision 3 Page 40 of 101

• Intake of St. Johns wort, Carbamazepine, extracts from Gingko, artemisinin, enzalutamide, efavirenz, lopinavir, ritonavir, tipranavir, rifampicin as they are relevant CYP2C19 inducers.

• Initiation of non-prescription drugs or vitamins including medical nutrition formulations. However if such medications were initiated before Visit 1, then they can be continued concomitantly during the study.

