A substantial body of EEG studies supports the hypothesis that schizophrenia and AD are related to impaired neural synchrony and there is growing evidence that impaired sensory-processing significantly contributes to the cognitive deficits in these disorders (R14-3419; R14-3418; R14-3420). Sensory event-related potentials (ERPs) have also been widely used to examine basic neuronal activity in both normal brain function and in schizophrenia and Alzheimer's disease, and have revealed abnormalities in the basic processing of both repeated and novel environmental stimuli (R14-3433) and may be used as biomarkers of the diseases (R14-3416; R14-3417).

Furthermore, visual acuity disturbances were the most common BI 409306 drug related adverse events, based on the phase I studies data. Since the visual disturbances of the PDE5-inhibitor sildenafil are known to be caused by its PDE6 off-target activity and PDE6 enzyme is expressed in photoreceptor cells of the retina, BI 409306 was evaluated for potential activity against recombinant human PDE6 isoforms revealing no relevant activity (i.e. IC50 > $100~\mu M$). Additionally, BI 409306 was tested for potential affinity to 95 off-target receptors at $10~\mu M$ using binding assays showing no relevant activity.

In summary, based on preclinical in vitro data, visual disturbances do not seem to be linked to PDE6 or other off-target activity of BI 409306. Two preclinical studies have been conducted to elucidate an explanation for these phenomena.

Since no data are available on PDE9 protein expression in the retina, an immunhistochemical analysis was performed in the first preclinical study in order to assess PDE9 expression in retina cells of rat and human tissue. This study demonstrated specific staining of PDE9 expression in rat and human retina tissue, confirmed via both positive tissue control (cerebellum and kidney) and via negative control (absence of primary antibody; isotype

Page 16 of 101

control). There was widespread distribution of PDE9 in the rat and human retina except the outer segment of the photoreceptor layer.

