2.3 BENEFIT - RISK ASSESSMENT

The target structure (PDE9) for the compound BI 409306 is widely distributed in various tissues and organs but predominantly localized throughout the specific brain areas (hippocampus, cortex, olfactory bulb, striatum, thalamus, hypothalamus, amygdala, midbrain, cerebellum (R12-4412, R10-5402).

The enzymatic action of cyclic nucleotide PDEs is the primary mechanism for inactivation of cAMP/cGMP by hydrolyzing. Inhibition of PDE9 increases the intracellular availability of the second messenger cGMP and consequently could have a positive effect on several aspects of cognition, including information processing, attention, memory and executive functioning. Based on its mechanism of action and its preclinical profile, including the in vitro, in vivo pharmacology data, the data from toxicology studies in two species as well as the data obtained in the clinical studies (U12-1034, U12-2165, U13-1182), there is no indication that BI 409306 should be regarded as a high risk compound.

Overall, BI 409306 shows a favorable nonclinical safety profile. There was no genotoxic potential of BI 409306. The toxicological profile of BI 409306 is characterized by cardiac effects which seem to be consistent with those described for phosphodiesterase inhibitors in general. Previous clinical trials found that BI 409306 was well tolerated in young and elderly healthy subjects in single doses of 0.5 to 350 mg and multiple doses up to 100 mg once daily. The most frequent drug related adverse events were visual side effects that occurred shortly after dosing and mostly resolved within 1 hour. All adverse effects generally were restricted to high dose levels and were reversible (U12-1034; U13-1182; U12-2165; U13-1303). Cardiac function will be monitored during the study, along with a 24-hour ambulatory heart rate monitoring (cf. Flow Chart).

As with all drugs, the potential for hypersensitivity and allergic reactions have to be taken into consideration when BI 409306 is administered. Other risks are inherent to any early clinical trial such as unexpected adverse clinical or laboratory event. Although rare, a potential for drug-induced liver injury is under constant surveillance by sponsors and regulators. Therefore, this study requires timely detection, evaluation, and follow-up of laboratory alterations of selected liver laboratory parameters to ensure subjects' safety.

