3.3.3 Exclusion criteria

- 1. Presence of active ocular conditions with or without visual impairment due to any causes (e.g. cataract, chorioretinal macular lesion, amblyopia, active diabetic retinopathy, uncontrolled glaucoma, active inflammation or infection, etc.) in one eye or both eyes at the screening phase that may interfere with the ocular assessments or analyses and interpretation of the results from this study, in the clinical judgment of the investigator.
- 2. Planned ocular treatment (e.g. intravitreal antivascular growth factor, corticosteroids) or surgery during the study period.
- 3. Current or planned use of ocular or systemic corticosteroids.
- 4. Current or planned use of medications known to be toxic to the retina, lens, optic nerve (e.g. choroquine/hydrochoroquine, chlorpromazine, tamoxifen, desferoximine, etc.).
- 5. Subjects treated with more than two antipsychotic medications (including more than two dosage forms).
- 6. Subjects needing to take long-acting hypnotics or anxiolytic (i.e. Diazapam).
- 7. Subjects taking medications that are known to be strong or moderate CYP1A2 inhibitors (For a list of strong and moderate CYP1A2 inhibitors please consult the ISF Section 11 "Safety Information").
- 8. Dementia in AD patients, secondary to other disorders (based on clinical data and/or current laboratory findings and/or on a pre-existing cranial MRI or CCT which is not older than 12 months prior to screening visit)*, for example: small vessel disease, neurosyphilis, craniocerebral trauma.
 - *If it is not already available then a CCT scan must be performed at screening.
- 9. Neurological disease (other than Dementia of Alzheimer Type such as: Lewy body dementia primary diagnosis, Huntington's disease, Parkinson's Disease encephalitis, epilepsy, vascular or multi-infarct dementia, stroke, congenital mental deficiency, or multiple sclerosis), or mental retardation.

- 10. For AD patients, the following drugs are prohibited for 3 months prior to randomization and for the duration of the trial:
 - a. tricyclic antidepressants,
 - b. antidepressants that are monoamine oxidase inhibitors,
 - c. neuroleptics with moderate or greater anticholinergic potency (e.g., chlorpromazine, fluphenazine, loxapine, perphenazine, thioridazine),
 - d. anticholinergic medications.
 - e. Intake of St. Johns wort, Carbamazepine and extracts from Ginko as they are relevant CYP2C19 inducers.

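### Other phosphodiesterase inhibitors, sildenafil included, are barred by name only in AD patients, while the primary endpoint counts any subject with a treatment-emergent eye-disorder AE in all three populations

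*Protocol*

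**What the plan says.** Protocol Section 4.2.2.1 opens with rules for everyone. The first is a general clause: "Any medication that may interfere with the action of BI 409306 or whose action may be altered by concomitant administration of BI 409306" is not permitted during treatment and the 14-day follow-up, as the investigator judges. A limit on chronic corticosteroids follows, and then "Use of medications that are known to be strong or moderate CYP1A2 inhibitors is not permitted". After these come rules for patients with schizophrenia (CIAS), and then a list introduced by "For AD patients, intake of the following medications with the mentioned exceptions is prohibited during the entire duration of the trial including follow-up". The item "Intake of other phospodiesterase inhibitors (for example theophylline, roflumilast, sildenafil, tadalafil, vardenafil, avanafil" is in that last list. Healthy volunteers (HV) have no list of their own.

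No exclusion criterion in Section 3.3.3 names the class. The nearest, criterion 4, concerns drugs toxic to the retina, lens or optic nerve, and none of its examples is a phosphodiesterase inhibitor. Section 3.3.4.1 requires withdrawal from treatment if "The patient needs to take concomitant drugs that interfere with the investigational product(s), in the clinical judgment of the investigator".

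On pharmacology, Section 1.1 states: "Since the visual disturbances of the PDE5-inhibitor sildenafil are known to be caused by its PDE6 off-target activity". It adds that BI 409306 showed no relevant PDE6 activity, but that in rat retina it raised the electroretinogram A- and B-waves and ganglion-cell activity much as sildenafil did. Section 2.3 states: "The toxicological profile of BI 409306 is characterized by cardiac effects which seem to be consistent with those described for phosphodiesterase inhibitors in general".

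The primary endpoint (Protocol 5.2.1, SAP 5.1) is the number and percentage of subjects with AEs in the Eye disorders class, with no condition on drug-relatedness. The secondary AE endpoint does carry that condition. Protocol 7.3.1 and SAP 7.8.1 base AE analysis on events from first dose to 7 days after the last, and SAP 7.8.1 counts subjects, not events.

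**The concern.** A drug that the protocol describes as causing visual disturbances is expressly forbidden in one population and not in the other two, although the event of interest is visual. An eye AE caused by sildenafil in a healthy volunteer or CIAS patient would enter the primary count like any other.

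This matters most for the volunteers. Protocol 2.1 makes comparison with them a purpose of the trial, and Protocol 3.2 calls them the control. SAP 6.1 provides layouts that put AD beside HV (the 7-column and 4-column displays) and AD beside its age-comparable volunteers (HV_AD). The SAP does not say which layout the eye-disorder table will use. Wherever AD and HV are read together, one side has the named bar and the other does not. Any distortion would tend to raise the HV proportion and so make an excess in AD look smaller.

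There is also a safety side. Taking a second phosphodiesterase inhibitor with BI 409306 stacks drugs whose cardiac effects the protocol itself links.

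**Working it through.** **Subjects outside the named bar.** Protocol 7.6 plans 20 HV, 20 AD and 20 schizophrenia patients: 3 × 20 = 60. By cell, 3 populations × 2 doses × 10 = 60, so the plan's total is reproduced. Outside the bar: 60 − 20 = 40, and 40/60 = 66.7%.

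**Weight of one extra affected subject** (100/n):

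| Group | n | Points |
|---|---|---|
| HV_AD (5 low-age + 5 high-age, Protocol 3.3.2) | 10 | 10 |
| One population in one dose group | 10 | 10 |
| All HV | 20 | 5 |
| One dose group | 30 | 3.3 |

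**Possible size.** The documents give neither a rate of use nor a rate of eye AEs among users, so both are assumed:

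- u, the share of non-AD subjects who use such a drug and are not stopped under the general clause: 0 to 10%.
- v, the share of users with an eye AE from it in the treatment-emergent window: 5 to 20%.
- No users in AD.

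Then p = u × v, the expected number is n × p, and the chance of at least one is 1 − (1 − p)^n.

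| u | v | p | Expected in 20 HV | At least one in 20 HV |
|---|---|---|---|---|
| 0 | any | 0 | 0 | 0 |
| 1% | 5% | 0.0005 | 0.01 | 1.0% |
| 5% | 20% | 0.01 | 0.2 | 18.2% |
| 10% | 20% | 0.02 | 0.4 | 33.2% |

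At the top of the range, the 10 HV_AD have an expected 0.2 cases and an 18.3% chance of at least one. The 40 non-AD subjects have an expected 0.8 and a 55.4% chance. The expected rise in the HV proportion is 100p, or 0 to 2 points. These are upper figures for the given u and v: because subjects are counted once, a user who would have had an eye AE from BI 409306 anyway adds nothing.

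**Which contrasts are touched.** Dose is randomised 1:1 within each population group (Protocol 4.1.2), so use should fall evenly on 25 mg and 100 mg apart from chance. CIAS and HV_CIAS are under the same rule. AD against HV, and AD against HV_AD, are not.

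**Is there an AD-specific reason?** The item speaks of other phosphodiesterase inhibitors, so it refers to the class of the study drug. The retinal and cardiac statements in Sections 1.1 and 2.3 are about pharmacology and toxicology, not about AD. The protocol gives no reason for the limit.

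**The case against.** The strongest reply is that all subjects are already covered. The general clause forbids interfering drugs throughout treatment and follow-up, withdrawal for such drugs is mandatory, and Section 1.1 gives an investigator good grounds to apply both to sildenafil. This stands in part: a reader might infer that the plan permits sildenafil in volunteers and CIAS patients, and it does not say so. But applying the clause is a matter of judgment. The clause already applied to AD patients as well, yet six drugs were still named for them.

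A second reply is that not every rule based on study-drug pharmacology is general. A reader might take the CYP1A2 rule, which covers everyone in both Section 4.2.2.1 and Section 3.3.3 ("Subjects taking medications that are known to be strong or moderate CYP1A2 inhibitors"), as the pattern from which the phosphodiesterase item departs. The documents do not support that. The CYP2C19-inducer restriction concerns the main metabolic enzyme of BI 409306 and is also AD-only, in Section 4.2.2.1 and in exclusion 10e. The point therefore rests on the visual and cardiac statements alone.

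Third, the affected contrast is weak already. AD and HV differ in disease and in permitted co-medication, there is no test or decision rule, and the groups are small. If the true HV proportion were 10 to 20% (an assumption), its standard error with n = 20 would be √(0.1 × 0.9/20) = 6.7 to √(0.2 × 0.8/20) = 8.9 points, against an expected shift of at most 2. This stands, and it limits the weight of the point.

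Fourth, other data would help to recognise a case. Causality is judged with co-medication in mind (Protocol 5.2.2.1) and tabulated (7.3.3), drug-related AEs are a secondary endpoint, and co-medication is summarised (SAP 7.2). That is true, but none of it changes the primary count.

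**Conclusion.** The point holds as a worthwhile low-cost improvement. The named bar covers 20 of 60 planned subjects, and for the other 40 the class is left to judgment, although the primary endpoint ignores cause and the protocol records sildenafil's visual effects. What is exposed is subject safety and the descriptive, non-randomised reading of AD against HV.

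A reader might go further and infer that the primary analysis or the dose comparison is biased. The documents do not support this: the randomised dose contrast is not systematically affected, CIAS against HV_CIAS is even, and nothing shows that any subject uses such a drug. The effect may be zero. The upper figures (a 2-point expected rise and a 33% chance of at least one case in HV) rest wholly on the assumed rates. Only the weight of a single case, 5 points of HV or 10 points of HV_AD, follows from the plan itself.

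**What to change.** **Protocol.** In Section 4.2.2.1, move the phosphodiesterase-inhibitor item out of the AD list and place it in the common paragraph directly after the CYP1A2 line. Keep its present duration, the entire trial including follow-up.

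**SAP.** Add the class to prohibited-medication violation D1 in Table 6.2: 1, which now lists only the CYP2C19 inducers, so that use is flagged. D1 looks only at the 3 days before Day 1 and/or Day 14. For this class the window should be the whole period of the bar, because an eye AE can fall on any treatment day. The catch-all Z3 could take such a case, but only after the fact. Keep the exclusion column at none: users stay in the treated set and in the primary count.

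**Cost.** One moved item and one added entry in a table, with no new procedure, data field or output. The downside is that a few otherwise eligible CIAS patients or volunteers who take such a drug may be lost.
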